6.2.1.2.2 Grading of Troponin-I Elevation

Central testing of cardiac troponin-I will be performed for eligibility **confirmation**, grading, and withholding decisions. The following criteria is developed based on CTCAE 4.0 to determine the grade of troponin-I elevation with ADVIA Centaur XP TnI assay performed by central lab:

- grade 1: isolated elevation of troponin > 99th percentile URL of 0.04 ng/mL for females and 0.059 ng/mL for males
- grade 3: troponin elevation greater than or equal to manufacturer's defined cut-off for MI of 0.78 ng/mL

6.2.2 Dosage Adjustments, Delays, Rules for Withholding or Restarting, Permanent Discontinuation

6.2.2.1 Amgen Investigational Product: AMG 176

The reason for dose change of AMG 176 is to be recorded on each subject's CRF(s).

Dosage Adjustments

Upon completion of the ramp-up dosing if applicable, the subject should continue on the same target dose of AMG 176 throughout the study unless the following events occur:

- For subjects experiencing an adverse event meeting the DLT definition or intolerable related adverse events BUT showing evidence of response, there will be an option to reduce the dose to the immediate next lower dose level shown to be safe and tolerable in the dose escalation part of the study.
 - The study drug can be resumed once the adverse events recover to baseline or grade 1 and the reintroduction of AMG 176 is deemed safe by the site investigator and Amgen's Medical Monitor.
 - Subjects must be informed of the risk of continuing on therapy. Each subject is only allowed a single dose reduction. Subjects showing evidence of response or subjects who in the opinion of the investigator may be responding to AMG 176, may have the option to have more than single dose reduction if deemed safe by the site investigator and Amgen's medical monitor.
- Subjects who experience grade 3 arrhythmia possibly associated with AMG 176, AMG 176 dosing must be resumed at the immediate next lower dose level if the requirements mentioned below in Rules for Restarting are met.
- For subjects meeting the withholding criteria for elevation of cardiac troponin (> 0.1 ng/mL), AMG 176 dosing can be resumed at the immediate next lower dose level if the requirements mentioned below in Rules for Dose Withholding are met.

Subjects should not be re-challenged with AMG 176 if the following AMG 176-related adverse events occur:

- Any life-threatening adverse events
- Drug-induced liver injury (DILI) meeting Hy's law
- Persistent grade 3 adverse events that do not recover to baseline or grade 1 within 4 weeks.
- Any AMG 176 related adverse event meeting DLT-criteria that recurs despite 2 dose level reductions

Dosage Delays

During the DLT evaluation period, if the dosing is delayed for more than 2 weeks the subject will be removed from the study and will be replaced. After DLT evaluation period, if the dosing is delayed for < 4 weeks, the subject should resume the treatment as soon as possible if deemed safe by the investigator. The investigator should inform the Amgen Clinical team as soon as the unexpected dosing interruption occurs. If the dosing of AMG 176 is delayed > 4 weeks (missing 1 cycle) due to AMG 176 related adverse events, the subject will be permanently removed from AMG 176 treatment. If the dosing delay occurred under conditions other than those associated with AMG 176 related toxicities, the case will be reviewed by Amgen medical monitor to determine whether the subject will be allowed to resume AMG 176 treatment.

Rules for Dose Withholding

AMG 176 should be withheld for any of the following:

- Suspected DLT (including adverse events that meet DLT definition outside DLT observation period).
- Aspartate aminotransferase or ALT greater than $3 \times$ ULN or total bilirubin greater than $1.5 \times$ ULN.
- Any grade 3 arrhythmia deemed possibly related to AMG 176. Should dosing be resumed, AMG 176 should be given at the next lower dose level.
- Any central lab elevation of cardiac troponin > 0.1 ng/mL (ADVIA Centaur XP manufacturer's prognostic cut-off) OR any change in the clinical status, above lab analytes (central or locally obtained), echocardiogram, or ECG deemed significant by the investigator or study subjects' care team.
- Upon meeting withholding criteria for AMG 176, investigator/site physician should evaluate appropriateness of apparent benefit vs risk of re-initiating AMG 176. Based on the assessment, a subject may be continued drug at a reduced dose or permanently discontinue therapy.
 - Low elevations from 0.04 ng/mL for females or 0.059 ng/mL for males to ≤ 0.1 ng/mL do not require withholding or dose reductions, though troponins should be monitored with subsequent doses.

- Elevations > 0.1 ng/mL should result in a dose withholding, and if further treatment is considered, should be restarted at one dose level below the dose where elevated troponins were observed
- Any consideration for continued treatment of AMG 176 after troponin elevations will require discussion between the investigator, subject, and Amgen medical monitor, and following normalization of all abnormalities.
- Study subjects that meet withholding criteria require continuous cardiac monitoring (telemetry) for at least 24 hours, and a cardiologist's evaluation that includes transthoracic echocardiography to assess the study subject and provide recommendations for further cardiac care. Monitoring should continue according to local SOC.

Rules for Restarting

AMG 176 dosing can be resumed:

- If the adverse event resolves to grade ≤ 1 or return to subjects' baseline values.
- For subjects meeting the withholding criteria for elevation of cardiac troponin (> 0.1 ng/mL), AMG 176 dosing can be resumed at the immediate next lower dose level if the requirements mentioned above in Rules for Dose Withholding are met.
- If the restarting of therapy should be deemed safe by the site investigator and Amgen's medical monitor.

Rules for Permanent Discontinuation

Subjects will permanently discontinue from the investigational product if the following are observed:

- Subjects experience adverse events meeting the DLT criteria at any time. Subjects will be followed until the DLT is resolved, returns to baseline value or is considered stable. Subjects will be withdrawn from AMG 176 treatment and will be treated as deemed appropriate by the investigator or treating physician. Except for:
 - Subjects showing evidence of response or subjects who in the opinion of the investigator may be responding to AMG 176, may have the option to continue therapy once the adverse events recover to baseline or grade 1 and the re-introduction of AMG 176 is deemed safe by the investigator, and Amgen's medical monitor. The subject should restart at a reduced dose.
 - Intolerance of AMG 176
 - Grade 3 central laboratory elevations of troponin
 - Any grade 4 arrhythmias possibly associated with AMG 176
 - Symptoms of clinically significant cardiac dysfunction, ECG changes, or diagnostic evidence of decreased cardiac function or cardiac injury irrespective of any cardiac troponin level (centrally or locally obtained). Study subjects that meet permanent discontinuation criteria require continuous cardiac monitoring (telemetry) for at least 24 hours, and a cardiologist evaluation that includes transthoracic echocardiography to assess the study subject and provide

recommendations for further cardiac care. Monitoring should continue according to local SOC.

- Hepatotoxicity (as defined in Section [11.7](#))
- The dosing is delayed > 4 weeks due to AMG 176-related adverse events

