6.2.1.2 Definition of Dosage Limiting Toxicities

A DLT will be defined as any of the events described below occurring in a subject during the DLT evaluation period and regarded by the investigators and/or Amgen medical monitor to be related to AMG 176.

Any adverse event occurring outside the DLT evaluation period that is determined by the investigator to be possibly related to the investigational product, which is seen more frequently or is more severe than expected or is persistent despite appropriate management, can be determined to be a DLT upon unanimous decision by the DLRT after review of the adverse event and all available safety data. The grading of adverse events will be based on the guidelines provided in the CTCAE version 4.0 (available online at <http://evs.nci.nih.gov/ftp1/CTCAE/About.html>). For troponin elevation, refer to Section 6.2.1.2.2 for CTCAE grading interpretation. Determination of the severity of adverse events will be consistent with CTCAE version 4.0. The relationship of an adverse event to investigational product will be determined by the investigator. An event should be considered related to treatment if, in the investigator's medical judgment, there is a reasonable possibility that the event may have been caused by AMG 176.

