6.2.2.2.3 Management of Cardiac Arrhythmia

Subjects with risk factors for, or evidence of, existing heart disease should be closely monitored throughout their treatment with AMG 176. Subjects should be clinically monitored on ongoing basis for cardiac function (blood pressure, heart rate, ECHO, and ECG) according to the schedule of assessments (see Section 1.3). The administration of AMG 176 should be withheld if grade 3 or 4 arrhythmias (including tachycardia) develop or appear to be exacerbated by AMG 176 treatment. For any grade 3 arrhythmia related to AMG 176 administration, the AMG 176 dose should be reduced. Treatment may be resumed once the signs and symptoms resolve to baseline value or grade 1. Management should be tailored to the appropriate treatment for the underlying cardiac disorder according to the local SOC and institutional guidelines. For any grade 4 arrhythmia related to AMG 176 administration, AMG 176 should be permanently discontinued.

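### In AML, a recovered AMG 176-related grade 3 arrhythmia in a subject not thought to be responding comes under both a reduced-dose restart rule and a permanent discontinuation rule, with no stated precedence

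*Protocol*

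**What the plan says.** Six places in the protocol bear on a grade 3 arrhythmia attributed to AMG 176.

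- **Section 6.2.2.1, Dosage Adjustments.** "AMG 176 dosing must be resumed at the immediate next lower dose level if the requirements mentioned below in Rules for Restarting are met". The bullet before it, on events meeting the DLT definition, offers dose reduction only to subjects with evidence of response. The arrhythmia bullet has no such condition.
- **Section 6.2.2.1, Rules for Dose Withholding.** AMG 176 is withheld for a possibly related grade 3 arrhythmia, then: "Should dosing be resumed, AMG 176 should be given at the next lower dose level". Once withholding criteria are met, the physician weighs benefit against risk, and the result may be a reduced dose or permanent discontinuation.
- **Section 6.2.2.1, Rules for Restarting.** Dosing can be resumed "If the adverse event resolves to grade ≤ 1 or return to subjects' baseline values" and "If the restarting of therapy should be deemed safe by the site investigator and Amgen's medical monitor".
- **Section 6.2.2.2.3, Management of Cardiac Arrhythmia.** "For any grade 3 arrhythmia related to AMG 176 administration, the AMG 176 dose should be reduced". Treatment may resume after recovery; permanent discontinuation is tied to grade 4.
- **Section 6.2.2.1, Rules for Permanent Discontinuation.** AMG 176 stops permanently when "Subjects experience adverse events meeting the DLT criteria at any time", with an exception for subjects who are responding or whom the investigator thinks may be. Separate items name grade 4 arrhythmia and "Symptoms of clinically significant cardiac dysfunction, ECG changes, or diagnostic evidence of decreased cardiac function".
- **Sections 6.2.1.2 and 6.2.1.2.1, Table 6-1.** A DLT must be "regarded by the investigators and/or Amgen medical monitor to be related to AMG 176". In the AML column, a non-hematologic event of grade 3 or higher qualifies unless it clearly results from the leukemia. The AML exceptions cover weight change, gastrointestinal events, electrolytes, lipase, infection, fatigue and constipation, but not arrhythmia.

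**The concern.** One recovered event appears to fall under a rule that provides for restarting and a rule that requires stopping. Cardiovascular toxicity is a listed potential risk (Section 2.3.2.3), and the protocol limits further study to 240 mg/m² or less to avoid potential cardiac toxicity (Section 4.1.1). This is an area where the treatment rule should be unambiguous. Two sites could each follow a written instruction and act differently on the same facts. The choice also reaches the reported results: the SAP tabulates adverse events leading to withdrawal of AMG 176 (Section 9.6.2) and dose modifications with their reasons (Section 9.6.8). The same event could appear in either table depending on which rule was followed.

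**Working it through.** No arithmetic applies. The check follows one event through each rule: an AML subject with a grade 3 arrhythmia judged related to AMG 176.

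**Step 1: is it an event meeting DLT criteria?** It is non-hematologic, grade 3 and related. Under Section 8.2.4.2, a reasonable possibility counts as related, so an event possibly associated with AMG 176 will ordinarily meet the relatedness requirement too. Unless it clearly results from the leukemia, it meets the AML criterion in Table 6-1, and no AML exception removes it. The discontinuation rule applies DLT criteria at any time, so onset after the DLT window does not exempt it.

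**Step 2: apply the rules.** The two relevant conditions in Rules for Restarting (recovery, and a safety judgement) are read as both being required.

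| Situation | Arrhythmia provisions (Dosage Adjustments, 6.2.2.2.3) | DLT discontinuation rule | Result |
|---|---|---|---|
| Not recovered, or restart not judged safe | Restart conditions not met | Stop, subject to the response exception | No conflict |
| Recovered, judged safe, responding or possibly responding | Restart at a reduced dose | Exception allows restart at a reduced dose | Consistent |
| Recovered, judged safe, not thought to be responding | Restart at a reduced dose | Permanent discontinuation | Conflict |

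The Rules for Dose Withholding give a third answer in the last row: a benefit-risk judgement that can end either way, again with no response condition.

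**Step 3: look for precedence.** None is stated. The discontinuation list names arrhythmia only at grade 4, which hints that grade 3 was meant to be handled differently. But grade 3 troponin elevation is both a DLT in Table 6-1 and a separate item in that list, so separate listing of a cardiac event does not show that it lies outside the DLT rule.

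**Step 4: compare the verbs.** Dosage Adjustments uses must; Section 6.2.2.2.3 uses should for the reduction and may for resumption; Rules for Restarting uses can; Rules for Dose Withholding is conditional.

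**The case against.** The best defence is that must fixes the dose level and does not compel a restart. The bullet depends on Rules for Restarting, which include a safety judgement by the investigator and medical monitor. The withholding rule and Section 6.2.2.2.3 both treat resumption as optional. This is a fair reading, and it defeats any claim that the protocol forces treatment to resume. It does not remove the conflict: even as a gated option, restart is open under the arrhythmia provisions and closed under the DLT rule for the subject in the last row.

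A second defence is that the specific arrhythmia rule displaces the general DLT rule. That may be the intention, but the text does not say so.

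Stronger readings are tempting, and the documents do not support them.

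- **ECG changes.** A reader might infer that a grade 3 arrhythmia is also an ECG change requiring discontinuation, so that responders are caught too. The text does not say the term includes it. The item opens with clinically significant dysfunction, the withholding rule treats an ECG change deemed significant as a reason to withhold, and the separate grade 4 arrhythmia item would be largely redundant on that reading.
- **Share of subjects.** A reader might subtract the CR/CRi rates in Section 4.3.3 from one (1 − 0.094 = 0.906; 1 − 0.143 = 0.857) and conclude that some 85 to 90% of subjects with the event are affected. CR/CRi does not measure the exception, which also covers anyone the investigator thinks may be responding. It omits partial remission and morphologic leukemia-free state, which the SAP counts as response (Section 5). In Part 4, 38.1% had stable disease and 42.9% had no evaluable response, so that judgement cannot be read off the CR/CRi rate. No arrhythmia counts are given.
- **Comparability across cohorts.** One text governs all cohorts, and nothing ties the ambiguity to a particular cohort.

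**Conclusion.** The contradiction is real but narrow. It holds for an AML subject with a related grade 3 arrhythmia that recovers to grade 1 or baseline, whose restart is judged safe by the investigator and medical monitor, and who is neither responding nor thought to be responding. For that subject the arrhythmia provisions allow a reduced-dose restart, the withholding rule leaves the matter to judgement, and the DLT rule requires withdrawal.

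The conclusion rests on Table 6-1 as written for AML; the multiple myeloma column lists specific events, so the same argument is not made there. It does not depend on the ECG-changes item or on reading must as compulsion. How often the situation arises cannot be derived from the documents. The SAP tests no formal hypothesis (Section 2.2), so the consequence lies in consistent conduct and in descriptive counts of withdrawals and dose modifications, not in any inferential result. Which rule is clinically right is not a question for this review.

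**What to change.** Reconcile four parts of Section 6.2.2.1 (Dosage Adjustments, Rules for Dose Withholding, Rules for Restarting and Rules for Permanent Discontinuation) and Section 6.2.2.2.3 with Table 6-1. State whether the arrhythmia rule or the DLT discontinuation rule governs a related grade 3 arrhythmia, and whether the response condition applies. Say whether ECG changes, as used in the discontinuation list, includes grade 3 arrhythmia. Use one verb for resumption throughout. The sponsor and investigators should decide which rule applies.

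The cost is protocol wording only; no design or analysis element changes. SAP Section 10 records that the study was terminated early with a synopsis report. If dosing has ended, the useful equivalent is to identify any subject in this situation and report which rule was followed.

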- Wilson's disease and hemochromatosis
- nonalcoholic fatty liver disease including steatohepatitis
- non-hepatic causes (eg, rhabdomylosis, hemolysis)

If investigational product(s) is/are withheld, the subject is to be followed for possible drug induced liver injury (DILI) according to recommendations in the last section of this appendix.

Rechallenge may be considered if an alternative cause for impaired liver tests (ALT, AST, ALP) and/or elevated TBL, is discovered and the laboratory abnormalities resolve to normal or baseline (see next section in this appendix).

Table 11-4. Conditions for Withholding and/or Permanent Discontinuation of Amgen Investigational Product and Other Protocol-required Therapies Due to Potential Hepatotoxicity

Analyte	Temporary Withholding	Permanent Discontinuation
TBL	> 3 × ULN at any time	> 2 × ULN OR
INR	--	> 1.5 × (for subjects not on anticoagulation therapy) AND
AST/ALT	> 8 × ULN at any time > 5 × ULN but < 8 × ULN for ≥ 2 weeks > 5 × ULN but < 8 × ULN and unable to adhere to enhanced monitoring schedule OR > 3 × ULN with clinical signs or symptoms that are consistent with hepatitis (such as right upper quadrant pain/tenderness, fever, nausea, vomiting, and jaundice)	In the presence of no important alternative causes for elevated AST/ALT and/or TBL values > 3 × ULN (when baseline was < ULN)
ALP	> 8 × ULN at any time	--

ALP = alkaline phosphatase; ALT = alanine aminotransferase; AST = aspartate aminotransferase;

INR = international normalized ratio; TBL = total bilirubin; ULN = upper limit of normal

Criteria for Rechallenge of Amgen Investigational Product and Other Protocol-required Therapies After Potential Hepatotoxicity

The decision to rechallenge the subject is to be discussed and agreed upon unanimously by the subject, investigator, and Amgen medical monitor.

If signs or symptoms recur with rechallenge, then AMG 176 is to be permanently discontinued. Subjects who clearly meet the criteria for permanent discontinuation (as described in [Table 11-4](#)) are never to be rechallenged.

Drug-induced Liver Injury Reporting and Additional Assessments

Reporting

To facilitate appropriate monitoring for signals of DILI, cases of concurrent AST or ALT and TBL and/or INR elevation, according to the criteria specified in the above, require the following:

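### Protocol Sections 6.2.2.1 and 11.7 set different liver-test rules for AMG 176 and are not reconciled: the restart conditions conflict, and the bilirubin trigger makes no allowance for Gilbert's subjects

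*Protocol*

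**What the plan says.** Section 6.2.2.1, Rules for Dose Withholding, lists "Aspartate aminotransferase or ALT greater than $3" times ULN, "or total bilirubin greater than $1.5" times ULN, as a reason to withhold AMG 176. Nothing is said about cause, duration, symptoms or Gilbert's syndrome.

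Under Rules for Restarting, the same section allows dosing to resume "If the adverse event resolves to grade ≤ 1 or return to" baseline, and "If the restarting of therapy should be deemed safe by the site investigator" and the medical monitor. It cites Section 11.7 only under permanent discontinuation, as "Hepatotoxicity (as defined in Section" 11.7.

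Section 6.2.3, headed Hepatotoxicity Stopping and Rechallenge Rules, consists of a referral to Section 11.7 and does not mention 6.2.2.1. Table 6-1 sends Hy's Law cases to 6.2.3.

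Section 11.7 (Appendix 7) applies when no other cause of the liver changes has been identified. The temporary-withholding column of its Table 11-4 covers AMG 176 and other protocol-required therapies. The AST/ALT row has "> 8 × ULN at any time", then 5 to 8 times ULN if it lasts two weeks or more or if enhanced monitoring is not possible, then above 3 times with signs of hepatitis. Bilirubin and ALP have triggers above 3 and above 8 times ULN. On restart the section says "Rechallenge may be considered if an alternative cause for impaired liver tests" or raised bilirubin is discovered and the values return to normal or baseline. The decision is to be "agreed upon unanimously by the subject, investigator, and Amgen medical monitor".

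Criterion 109 in Section 5.1 waives the 1.5 times ULN bilirubin limit for subjects with Gilbert's syndrome.

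**The concern.** Two sets of rules cover the same drug and the same tests, and no sentence says which prevails. A site that starts at Table 6-1 or Section 6.2.3 is led to Section 11.7 and never meets the lower 6.2.2.1 thresholds, so it could go on dosing a subject whom 6.2.2.1 would have held. On restart the looser text is 6.2.2.1, so a site reading only that section could resume AMG 176 after an unexplained liver event where 11.7 offers no route back. The situation is foreseeable: Section 2.3.2.3 lists hepatobiliary toxicity as a potential risk, and Table 11-3 lists ALT and AST increases among expected events in AML. Withheld doses in cycle 1 also bear on DLT evaluability, which requires 75% of planned AMG 176 doses (Section 6.2.1.1).

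The Gilbert's gap is a separate matter. A subject who is eligible under criterion 109 can meet the withholding trigger at the entry value.

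**Working it through.** The plan gives no figure to reproduce, so the check sets the two texts side by side.

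Ratio of the triggers that carry no added condition, Table 11-4 over Section 6.2.2.1:

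- AST/ALT: 8 / 3 = 2.67
- Total bilirubin: 3 / 1.5 = 2.00

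These compare thresholds. They do not measure any effect on subjects.

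Test cases, assuming no other cause is identified except in the Gilbert's row:

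| Case | Section 6.2.2.1 | Section 11.7 |
|---|---|---|
| ALT 4 × ULN, no symptoms | Withhold (4 > 3) | No trigger: above 3 needs symptoms |
| ALT 6 × ULN for one week, enhanced monitoring in place | Withhold (6 > 3) | No trigger: under two weeks and monitored |
| Isolated bilirubin 2 × ULN | Withhold (2 > 1.5) | No trigger (2 < 3) |
| ALP just above 8 × ULN, alone | No trigger in the liver line | Withhold |
| Gilbert's subject entered at bilirubin 2 × ULN | Withhold at the entry value | Outside the rules: Gilbert's is a listed alternative cause |
| Withheld for ALT > 8 × ULN, no cause found, recovered to grade 1 | Restart possible if investigator and medical monitor deem it safe | No route to rechallenge |

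The first three rows show 6.2.2.1 stricter on AST/ALT and bilirubin. The ALP row runs the other way. When another cause is identified, Table 11-4 does not apply at any value, while 6.2.2.1 still withholds.

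The last row is where the texts give opposite answers, and three limits apply to it:

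1. Section 6.2.2.1 itself bars rechallenge after AMG 176-related Hy's Law liver injury, life-threatening events, and grade 3 events that do not recover to baseline or grade 1 within 4 weeks.
2. In AML, a related non-hematologic event of grade 3 or higher is generally a DLT (Table 6-1), and a DLT leads to permanent discontinuation. The documents do not give the CTCAE liver cut-offs, so they do not show whether a value above 8 × ULN is grade 3. The second row is subject to the same uncertainty.
3. The DLT stop has an exception. Section 6.2.2.1 lets responders, and subjects who may be responding, restart at a reduced dose once recovered to baseline or grade 1, with no alternative cause required. The conflict with 11.7 therefore survives a DLT for those subjects.

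For the Gilbert's row, the return-to-baseline wording in the restart rule gives a way back to dosing, but it does not switch off the trigger, which remains met while the subject sits at baseline.

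**The case against.** The strongest reply is that the sections can be read together. The 6.2.2.1 withholding list is unconditional, and Table 11-4 adds triggers without ever telling a site to dose below them. Section 11.7 also has a narrower scope and is headed as suggested actions. Section 6.2.2.1 cites 11.7 only for permanent discontinuation, which suggests that 6.2.2.1 governs withholding. The heading of 6.2.3 names rechallenge and points to 11.7, which suggests that 11.7 governs restart after liver injury. On that reading 6.2.2.1 is the general rule and 11.7 the specific one.

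On withholding this stands. A reader might infer a direct contradiction there, but a site that holds at the lower value complies with both texts. A reader might also infer that nothing in the protocol hints at precedence, and that is too strong given the heading of 6.2.3.

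On restart the reply only partly stands. A heading and a bare referral do not displace an explicit restart rule in 6.2.2.1, and they do not settle the position of a subject withheld under 6.2.2.1 who never met Table 11-4. The 11.7 sentence is worded as a permission, but it is the only route to rechallenge that section offers.

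On Gilbert's, a reader might infer that these subjects are shut out of treatment. The return-to-baseline route means they are not. The literal trigger still applies to them.

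**Conclusion.** The point holds as a minor drafting defect with a safety aspect. On withholding there is no contradiction, only a looser table that a site may reach first. On restart the two texts conflict in the cases left over after the 6.2.2.1 bars on rechallenge, including some responders after a DLT. The Gilbert's gap is literal but has a partial remedy.

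The documents give no frequency for the relevant liver values, so the number of subjects affected cannot be estimated. The documents do not support inferring that any subject was harmed or that any result changes. Section 11.7 puts AST/ALT above 3 times ULN under close observation with repeat tests within 24 hours, Section 4.2.1 replaces subjects who are not DLT-evaluable during dose escalation, and SAP Section 10 records that the study was terminated early. The conclusion rests on reading the 11.7 rechallenge sentence as a condition and on there being no ranking sentence elsewhere in the protocol; none was found.

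**What to change.** State in Section 6.2.3 and again above Table 11-4:

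- AMG 176 is withheld if either a Section 6.2.2.1 liver threshold or a Table 11-4 trigger, including ALP, is met.
- A subject who met a Table 11-4 withholding criterion may restart only under the Section 11.7 rechallenge conditions. Otherwise the 6.2.2.1 restart rule applies. The 6.2.2.1 bars on rechallenge apply in every case.

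In the 6.2.2.1 bilirubin line, replace the 1.5 times ULN total bilirubin trigger for Gilbert's subjects with a limit relative to baseline or based on direct bilirubin, and keep the AST/ALT and suspected-DLT triggers. A blanket exemption would be wrong: Table 11-4 already treats Gilbert's as an alternative cause, so these subjects could be left with no numeric bilirubin trigger at all.

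The cost is wording in three places, with possibly a few more withheld doses or fewer restarts. Sample size and analyses do not change. As the study has ended early, the practical use is in any extension or successor protocol that carries this text forward.

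### Protocol section 6.2.2.1 is inconsistent for grade 3 central troponin-I (0.78 ng/mL or more): two restart routes have no upper limit, one entry requires a permanent stop, and no precedence is stated

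*Protocol*

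**What the plan says.** The dosing rules are in Protocol section 6.2.2.1. Grading is in section 6.2.1.2.2 and the DLT criteria are in Table 6-1.

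- **Grading.** On the central assay, grade 1 begins above the 99th percentile upper reference limit (0.04 ng/mL for women, 0.059 ng/mL for men). Grade 3 begins at 0.78 ng/mL, the manufacturer's cut-off for MI. No grade 2 is defined.
- **Rules for Dose Withholding.** AMG 176 is held for a central troponin above 0.1 ng/mL. After that, "Elevations > 0.1 ng/mL should result in a dose withholding, and if further treatment is considered, should be restarted at one dose level below" the level that produced the elevation. Continuing requires a discussion among investigator, subject and medical monitor, "following normalization of all abnormalities".
- **Rules for Restarting.** For these subjects, "AMG 176 dosing can be resumed at the immediate next lower dose level if the requirements mentioned above in Rules for Dose Withholding are met". Dosage Adjustments gives the same permission "if the requirements mentioned below in Rules for Dose Withholding are met".
- **Responder route.** Dosage Adjustments (first bullet) and Rules for Permanent Discontinuation let a subject who meets DLT criteria but is responding, or in the latter section is thought to be responding, restart at a reduced dose. The event must have recovered to baseline or grade 1, and the investigator and medical monitor must consider it safe.
- **Rules for Permanent Discontinuation.** "Subjects will permanently discontinue from the investigational product if the following are observed", and the list that follows includes "Grade 3 central laboratory elevations of troponin".

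**The concern.** A subject whose central troponin-I reaches grade 3 and then returns to normal satisfies the conditions for restarting one dose level lower. The same subject appears on the list of those who must stop for good. The text never says which instruction governs. Section 6.2.2.2.7, on managing troponin elevation, names the assay for grading and withholding decisions but sets no order between the rules.

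Increased troponin is one of the drug's two identified risks (section 2.3.2), so this is a safety rule that sites should be able to apply in only one way. As written, two sites could handle the same result differently, and each could point to a clause in support.

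**Working it through.** There is no plan figure to reproduce. The check sets the threshold ranges side by side and then looks for a sentence that ranks them.

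**Inputs.** Withholding and resume threshold: above 0.1 ng/mL, no upper limit (6.2.2.1). Permanent stop: grade 3, which is 0.78 ng/mL or more (6.2.2.1 with 6.2.1.2.2). Both use the central laboratory result, so the assay does not separate them.

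**Overlap.** (0.1, ∞) ∩ [0.78, ∞) = [0.78, ∞).

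| Central troponin-I | Troponin resume rule | Grade 3 stop rule |
|---|---|---|
| up to 0.1 ng/mL | does not apply (no hold needed) | does not apply |
| 0.5 ng/mL (0.1 < 0.5 < 0.78) | applies | does not apply |
| 0.9 ng/mL (0.9 > 0.1 and 0.9 ≥ 0.78) | applies | applies |

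The lower edge of the overlap is 0.78/0.1 = 7.8 times the withholding threshold. It is 0.78/0.059 = 13.2 times the male reference limit and 0.78/0.04 = 19.5 times the female one.

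**Second route.** Table 6-1 makes a grade 3 troponin-I elevation a DLT for all subjects, and section 6.2.1.2 requires relatedness to AMG 176. A related grade 3 value therefore also meets the DLT entry in the discontinuation list, which has the responder exception. That exception does not mention troponin. The count is two restart routes (the troponin clauses and the responder exception) against two stop entries (the DLT entry and the grade 3 troponin entry). Capping only the troponin clauses would leave the responder route open.

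**What already narrows the gap.**

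- Cardiac symptoms, ECG changes or diagnostic evidence of cardiac injury require a stop at any troponin level.
- Withholding already triggers at least 24 hours of telemetry and a cardiologist's evaluation with echocardiography.
- Restart after a troponin elevation needs normalization and discussion with the medical monitor. Rules for Restarting also lists a safety judgement by both the site investigator and the medical monitor.
- For related events, a dosing delay beyond 4 weeks is a permanent stop, and a grade 3 event that has not recovered to baseline or grade 1 within 4 weeks bars rechallenge.

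What remains is an isolated grade 3 value that normalizes within 4 weeks and that both parties judge safe to re-dose.

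**The case against.** The strongest reply is that this is an ordinary broad hold with a narrower mandatory stop inside it. The resume text is permissive and conditional, while the stop text is obligatory, so a site that stops breaches neither. The withholding section itself allows either a reduced dose or permanent discontinuation. Other items follow the same pattern: suspected DLTs and raised transaminases are held without an upper limit, and DLTs and hepatotoxicity appear again as stop criteria. Footnote a of Table 6-1 offers further treatment only for grade 1. Much of this stands, and it makes the stop the more natural reading. It remains an inference, because footnote a is silent on grade 3 and no sentence limits the resume clauses. The change log for Amendment 14 describes the above-0.1 ng/mL wording as leaving restart open even at grade 3. A log cannot decide what the current text means, but it is a reason to ask the sponsor which rule is intended.

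A reader might also infer, from the text as extracted, that the grade 3 bullet falls under *Except for* and so is itself an exception to stopping. The neighbouring bullets do not support that. Grade 4 arrhythmia sits at the same level, and section 6.2.2.2.3 requires permanent discontinuation for it when related. The next bullet says "Study subjects that meet permanent discontinuation criteria require continuous cardiac monitoring (telemetry) for at least 24 hours". The indentation may be only an artefact of text extraction.

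A reader might further infer that the plan directs re-dosing after evidence of cardiac injury, or that dose-finding is compromised. Neither follows. Cardiac injury is a separate stop at any troponin level. The cohort rule in section 4.1.1, that one related grade 3 elevation forces de-escalation, does not depend on what happens to the individual subject.

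**Conclusion.** The inconsistency is real and confined to central troponin-I of 0.78 ng/mL or more. Values above 0.1 and below that level are covered by one rule only. Its weight is minor. The permanent stop is the more natural reading, and the residual case is the isolated, normalized grade 3 value described above. No event rate is estimated and no effect on any endpoint or DLT count is claimed.

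Exposure also limits it. Section 2.3.2.2 reports troponin elevations primarily at 360 and 480 mg/m² and no concerning elevations at 240 mg/m² or less, and section 4.1.1 restricts further investigation to 240 mg/m² or less. SAP section 10 states that the study ended early, so the correction would matter only for a subject still on treatment.

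The conclusion assumes that the grade 3 bullet is a stop criterion, as its neighbours indicate. It also takes the 4-week limits as they are written, for AMG 176-related events.

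**What to change.** State one governing rule for central troponin-I of 0.78 ng/mL or more.

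- **If grade 3 is meant to end treatment:** limit the resume wording in Dosage Adjustments, Rules for Dose Withholding and Rules for Restarting to values above 0.1 and below 0.78 ng/mL. State in Dosage Adjustments and Rules for Permanent Discontinuation that the DLT responder exception does not apply to grade 3 central troponin-I. Both changes are needed, because the first alone leaves the responder route open.
- **If restart after grade 3 is meant to be possible:** add one explicit exception to the grade 3 stop entry. It should require normalization of all abnormalities, a cardiology evaluation, medical monitor agreement and restart one dose level lower. Make the responder route subject to the same conditions.

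Change the list level of the grade 3 bullet only if the source document shows the same indentation.

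The cost is wording alone, with no new test or visit.
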